In **Year 1**, we plan to confirm our pilot findings suggesting that VA BIC is effective in reducing suicide risk after psychiatric hospitalization by conducting a small, randomized trial of VA BIC plus standard care versus standard care alone on the White River Junction (WRJ) VA Medical Center (VAMC) inpatient mental health unit (see Preliminary Studies section below). In addition, we plan to further adapt VA BIC for veterans experiencing three other high-risk care transition scenarios described above. During **Years 2 and 3**, we will sequentially conduct randomized trials of VA BIC plus standard care versus standard care alone for the other three high-risk care transition scenarios. If our findings indicate that VA BIC is an effective intervention in one or more of these high-risk care transition of VA BIC and assisting them with implementation at their sites. These materials would be used for broad dissemination in future work. Based on both our pilot work with the VA BIC and the results of the original international WHO BIC study, we are highly confident that our intervention will be helpful for rural VA facilities in decreasing suicide risk in at least one of the high-risk care transition scenarios. However, we feel that taking the preliminary steps in Years 1-3 will result in the most practical and effective program for rural VA facilities in Year 4.

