 - A) Clean and analyze data from trial of VA BIC for patients being discharged from an inpatient mental health unit.
 - B) Finalize VA BIC manual for patients being discharged from an inpatient mental health unit based on results.
 - C)Enroll 25 veterans in a randomized trial of VA BIC for patients being discharged from an inpatient medical/surgical unit after receiving psychiatric consultation.
 - D) Pilot an adapted version of VA BIC in 3 veterans being discharged from a residential substance treatment facility.
 - E)Enroll 13 veterans in a randomized trial of VA BIC for patients being discharged from a residential substance treatment facility.
 - F)Develop an adapted version of VA BIC for patients being discharged from an emergency room after presenting with a mental health concern.
- 3) Year 3: We will complete seven deliverables during the third year: (We will submit a study amendment prior to conducting the work described below)
 - A) Clean and analyze data from trial of VA BIC for patients being discharged from an inpatient medical/surgical unit after receiving psychiatric consultation.
 - B) Finalize VA BIC manual for patients being discharged from an inpatient medical/surgical unit after receiving psychiatric consultation based on results.
 - C)Enroll 12 veterans in a randomized trial of VA BIC for patients being discharged from a residential substance treatment facility.
 - D) Clean and analyze data from trial of VA BIC for patients being discharged from a residential substance treatment facility.
 - E) Finalize VA BIC manual for patients being discharged from a residential substance treatment facility.
 - F) Pilot an adapted version of VA BIC in 3 veterans following discharge from an emergency room after presenting with a mental health concern.
 - G)Enroll 25 veterans in a randomized trial of VA BIC for patients being discharged from an emergency room after presenting with a mental health concern.
- 4) Year 4: We will complete ten deliverables during the fourth year: (*We will submit a study amendment prior to conducting the work described below*)
 - A) Clean and analyze data from trial of VA BIC for patients being discharged from an emergency room after presenting with a mental health concern.
 - B) Finalize VA BIC manual for patients being discharged from an emergency room after presenting with a mental health concern.
 - C)Integrate VA BIC trial data across high-risk care transition scenarios and analyze results.

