We will perform a more complex analysis for the entire study sample at the end of the four years because we will have adequate power to do so. The following outlines are specific approach: Based on available evidence, we hypothesize that the VA BIC program plus standard hospital discharge care will lead to a significant reduction in suicidal ideation after discharge from an acute care setting. We believe that the effect of VA BIC on suicidal ideation will be the greatest at the three-month follow-up because the greatest intensity of follow-up care provided through VA BIC occurs within the first three months after discharge. We will generate descriptive summary statistics (e.g., means and standard errors, medians) and graphical displays for the BSS total scores at baseline and at each of the follow-up assessments. Because BSS scores are typically over dispersed, it is not appropriate to use standard parametric statistics. Therefore, we will treat the BSS scores as count data and use negative binomial regression. Specifically, we will use a generalized linear mixed model. We will consider allocation of study arm (categorical measure) and time (continuous measure) as fixed effects. Random effect will be used to account for correlation that arises from repeated measures of the same individual. We will assume a linear effect and model changes in suicidal ideation over time. We will calculate 95% CI and P-values and will define a *P*-value of < 0.05 to be statistically significant. We will use the maximum likelihood ratio to account for any missing data.

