Specific Aim 2: First, we will perform an analysis to demonstrate whether there are greater improvements in patient engagement, hopelessness, and perceived connectedness over time in patients assigned to the VA BIC intervention versus control condition at one, three months after discharge. For continuous variables measuring patient engagement (PIH, Hopelessness, Regularity of Care, Continuity of Care across Organizational Boundaries, and Intensity of Care) and perceived connectedness (INQ-15), we will generate descriptive summary statistics (e.g., means and standard errors, medians) and graphical displays for each measure at baseline and at each of the follow-up assessments. Second, using analysis of covariance (ANCOVA), we will calculate mean differences in scores for each of our continuous measures at the one-and three-month follow-up, as well as the associated 95% confidence intervals and *P*-values. For the categorical measure of disruptions in care, we will use chi-squared tests to compare the proportion of patients experiencing disruptions in care between the two study arms at one- month and three-months after discharge.

Specific Aim 3: While suicide deaths and suicide attempts are important clinical endpoints, this single-site trial will not be powered to detect a statistically significant effect between study arms. Furthermore, because we assume that few events will be observed in either arm, we plan to summarize our findings by providing basic descriptive statistics regarding the number of events in each arm at one-and three-month follow-ups.

Randomization: Prior to the start of study enrollment, the statistician will independently prepare allocation cards using a permutated block schedule. The advantage of this approach is that it ensures that an equal number of participants are assigned to each arm.⁵⁶ The statistician will the put these cards into sealed, opaque, numbered envelopes. The box of envelopes will be stored in a locked cabinet in the study coordinator's locked office.

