Sample Size: Because of our promising pilot work,¹ we believe it is appropriate to choose suicidal ideation as our primary outcome. In our pilot study, which included nine Veterans undergoing the VA BIC intervention, we found a greater than five-point improvement in the Beck Scale for Suicidal Ideation (BSS) over the three months following inpatient mental health discharge. Five points is a clinically meaningful improvement on the BSS as it represents the mean difference in suicidal ideation between ambulatory and hospitalized psychiatric patients.² Furthermore, with this sample size and level of improvement, we were able to demonstrate a significant difference in improvement in suicidal ideation compared to a matched group of historical controls participating in a post-mental health discharge qualitative study.^{1,3} Therefore, we will have sufficient power to show a clinically meaningful improvement in suicidal ideation overall and for each of the four high-risk care transition scenarios at one and three months after discharge if we enroll a total of 100 veterans (25 per transition scenario) over 3 years.

Study Population and Recruitment

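### The pooled BSS model omits care setting although it combines four sequential randomised trials; adding it would recover a little precision in the arm coefficient at almost no cost

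*Combined protocol and SAP*

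**What the plan says.** Specific Aims/Purpose describes one trial on the inpatient mental health unit in Year 1 and then gives the plan for the second and third years as follows: "we will sequentially conduct randomized trials of VA BIC plus standard care versus standard care alone for the other three high-risk care transition scenarios". The Year 4 deliverables include: "Integrate VA BIC trial data across high-risk care transition scenarios and analyze results". Sample Size sets the total: "if we enroll a total of 100 veterans (25 per transition scenario) over 3 years".

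For the entire sample, Specific Aim 1 under Statistical Considerations specifies a negative binomial mixed model. On its terms it says: "We will consider allocation of study arm (categorical measure) and time (continuous measure) as fixed effects". On correlation: "Random effect will be used to account for correlation that arises from repeated measures of the same individual". On the target: "We will assume a linear effect and model changes in suicidal ideation over time". No term for setting, scenario or trial is listed. Setting enters Aim 1 only through separate simple tests within each setting.

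For Aim 2 the plan says that, "using analysis of covariance (ANCOVA), we will calculate mean differences in scores for each of our continuous measures", with a chi-squared test for disruptions in care. It does not say whether these are pooled or run by scenario, and it does not list the ANCOVA covariates.

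The general rule under Statistical Analyses is to adjust only for baseline variables that differ significantly between arms.

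**The concern.** If patients are randomised within each scenario, the natural analysis conditions on scenario. The documents give some reason to expect different BSS levels. Ground East patients must have been admitted over acute self-harm risk, while Specific Aims/Purpose describes the residential group as any discharged patient and the emergency group as presenting with a mental health concern.

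A model with arm and time only treats setting differences as unexplained variation between patients. The arm coefficient is a between-patient comparison, so its standard error carries that extra variance.

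The significance-triggered adjustment rule will not repair this. With about 12 and 13 patients per arm in each scenario, a chi-squared test of setting by arm has eight cells, each 0.5 from an expected 12.5. The statistic is 8 × 0.25/12.5 = 0.16 on 3 degrees of freedom, nowhere near significance.

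At stake is some efficiency in the pooled analysis, and in any pooled Aim 2 comparison between patients.

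**Working it through.** **Inputs from the documents.** 100 patients, 25 per scenario; equal allocation (Randomization); visits at 0, 1 and 3 months; significance level 0.05 (taken as two-sided); 5 BSS points as the clinically meaningful improvement. The only between-group BSS gap given is also 5 points (Sample Size). **Assumed:** total SD 7 to 12, no dropout, 5 points as the between-arm difference, and the 5-point gap as a proxy for a difference between settings.

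**1. The plan's own figure.** Sample Size asserts enough power but gives no SD, power value or between-arm difference, so 100 can be neither reproduced nor refuted. With 50 per arm, power = Φ(5/(SD × √(2/50)) − 1.96).
- 80% power needs SD = 5/(2.8016 × 0.2) = 8.92.
- 90% power needs SD = 5/(3.2415 × 0.2) = 7.71.

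**2. Variance due to setting.** For a 5-point gap, the variance between settings is:
- one setting against three: 25 × ¼ × ¾ = 4.69;
- two against two: 25 × ½ × ½ = 6.25.

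At SD 8.92 (variance 79.6) these are 5.9% and 7.9% of the total.

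**3. Power for an arm comparison, without and with setting.** The adjusted SD is √(SD² − setting variance). At SD 8.92, one against three, it is √(79.57 − 4.69) = 8.65, and power is Φ(5/(8.65 × 0.2) − 1.96) = 82.4%.

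| Total SD | Setting omitted | Included, 1 v 3 | Included, 2 v 2 |
|---|---|---|---|
| 7 | 94.6% | 96.4% | 96.9% |
| 8.92 | 80.0% | 82.4% | 83.1% |
| 10 | 70.5% | 72.6% | 73.3% |
| 12 | 54.9% | 56.3% | 56.8% |

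The gain is 1.4 to 3.1 points. If setting explained 10% or 20% of the variance, power at SD 8.92 would be 84.0% or 88.0%.

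**4. Standard errors in a random-intercept linear model with three visits.** Take total variance 80 and intraclass correlation 0.4, so patient variance is 32 and residual variance 48.
- Arm coefficient, setting omitted: √((32 + 48/3)/25) = 1.386.
- Setting included, one against three: √((32 − 4.69 + 16)/24.96) = 1.317. Two against two: 1.293. Here 24.96 = 4 × 12 × 13/25.
- At intraclass correlation 0.6: 1.532 falls to 1.471 or 1.449. The reductions are 4% to 7% overall.
- Arm-by-time: the squared deviations of 0, 1 and 3 months sum to 4.667, so the standard error is √(48/(4.667 × 25)) = 0.641. Only residual variance enters, so setting changes nothing (0.524 with and without setting at correlation 0.6).

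**5. Simulation of the negative binomial mixed model.** Assumed: log link, random-intercept SD 0.7, negative binomial size 3, arm effect −0.18 per month on the log scale, 12/13 allocation within setting, likelihood-ratio tests, 800 runs. Power without → with setting:

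| Setting means | Arm coefficient | Arm-by-time |
|---|---|---|
| 14/9/9/9 | 20.2% → 22.0% | 69.5% → 69.8% |
| 14/14/9/9 | 20.1% → 23.0% | 68.5% → 68.8% |
| 16/12/8/4 | 17.9% → 25.2% | 67.8% → 67.4% |

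Under the null (240 runs), omitting setting did not inflate rejection. With 16/12/8/4 the arm test rejected 2.5% without setting and 5.8% with it. The Monte Carlo error is √(0.05 × 0.95/240) = 1.4 points, so this suggests conservatism at most.

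**6. Aim 2, if pooled.** Illustration with assumed mean visit counts and a within-setting SD of 4. Means of 8/6/4/4 have between-setting variance 2.75, so the unadjusted standard error is √(18.75/16) = 1.08 times as large. Means of 6/5/5/4 have variance 0.5, giving √(16.5/16) = 1.02.

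**The case against.** The strongest reply is that the model's stated purpose is change over time. For an arm-by-time contrast the patient random intercept already absorbs setting differences in level, and steps 4 and 5 confirm that nothing is gained. This stands. It limits the point to the arm coefficient, which is nevertheless the only treatment term the plan lists. The unlisted arm-by-time term is the larger matter: in these simulations testing arm alone gave about 18% to 25% power, against about 67% to 70% for arm-by-time. Including setting did no harm in either case.

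Second, every magnitude rests on assumed SDs and setting means. That also stands. A reader might infer that the settings will differ greatly in BSS, but no document gives BSS by setting. The Ground East design section limits medical-surgical recruits to those judged at risk for suicide, which points to smaller differences.

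Third, a reader might take setting to be a stated randomisation stratum. It is not: Randomization describes a permuted-block schedule and mentions no stratification. Separate randomisation by setting is inferred from the sequential trials in Specific Aims/Purpose and from the plan to open each location by amendment.

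Fourth, if the Aim 2 ANCOVA includes the baseline score, much of the setting difference in the scales is already removed. This is fair for those scales. It does not help visit counts, regularity of care or disruptions, which accrue after study entry.

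**Conclusion.** The point holds as a modest efficiency improvement. The pooled model omits the factor that defines the four trials it combines. For the arm coefficient this costs about 1 to 3 points of power, taking the 5-point gap as a proxy and SDs of 7 to 12. It costs more only if settings differ much more widely, and nothing for arm-by-time. Pooled Aim 2 comparisons between patients are exposed in the same way, by an amount the documents do not let one estimate.

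Three stronger readings are not supported:
- **That the test is invalid.** Neither bias nor excess false positives was found.
- **That the random effect is materially mis-specified.** The plan does not state its distribution, and no harm beyond lost precision has been shown.
- **That this is the only analysis the plan calls adequately powered.** Specific Aim 1 says so of the pooled analysis, but Specific Aims/Purpose, Preliminary Studies and Sample Size also claim enough power for each scenario.

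**What to change.** In Statistical Considerations, Specific Aim 1, add transition scenario (four levels) as a fixed effect in the pooled BSS model. In Specific Aim 2, state whether the analyses are pooled. Where they are, include scenario in each ANCOVA and replace the chi-squared test for disruptions in care with a Cochran-Mantel-Haenszel test stratified by scenario. State also whether each scenario has its own randomisation schedule.

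The cost is a few sentences of text and three degrees of freedom out of 100 patients. Scenario is known for every patient, so no new data are needed. The change should be written in before the first scenario's data are analysed in Year 2, so that it cannot look like a choice made after seeing results.

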sensitive to clinical change, and unlike most other measures of suicidal ideation, higher scores on the BSS are associated with death by suicide. While there is no established BSS cutoff score to classify suicide risk as high, low, or none, there is evidence that higher scores on the BSS correspond to more severe suicidal ideation.^{2,39} There is evidence that an improvement of five points or more on the total BSS scores may be clinically relevant.²

Secondary Outcome (Patient Engagement): We will measure patient engagement in treatment at baseline and at follow-up assessments. Patient engagement is a complex phenomenon to measure.⁴⁰ The term 'patient engagement' encompasses various aspects of care related to a patient's motivation and intent to be an active participant in addressing their healthcare needs.⁴⁰ To date, there is no agreed-upon measure in the literature that incorporates all aspects of the experience of 'patient engagement.⁴⁰ In the field of mental health, there is some notion that 'patient engagement' should mean that a patient experiences collaborative care, feels supported during their treatment, and adopts 'good practices' or behaviors that support their overall well-being.⁴⁰⁻⁴¹ Therefore, only assessing whether a patient attended a mental health appointment may not adequately reflect treatment engagement. There is also evidence that symptom severity can preclude patients from engaging in care.⁴² Pfeiffer *et al.* found that, despite improvements in timely outpatient follow-up after VA psychiatric hospitalization, there were no significant changes in readmission or antidepressant treatment.⁴³ In fact, Bernet *et al.* found that appointment intensity was higher in Veterans who reattempted suicide after discharge versus those who did not reattempt.⁴⁴ Thus, we conceptualize that engagement includes continuity of care and activation.

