- All patients (including patients randomized to VA BIC) will have access to standard psychiatric hospital discharge care. Furthermore, regardless of study assignment, all patients will undergo outcome assessment at baseline (0M), one month (1M) and three months (3M). These assessments will be conducted by the independent outcome assessor. The independent outcome assessor will conduct the baseline assessment in a private office on GE around the time of discharge. We anticipate that, in most cases, the baseline assessment will occur on the day before discharge. Depending on patient preference, the independent outcome assessor will conduct the follow-up assessments in a private office on the WRJ VAMC campus or over the phone (or VA Video Connect). The assessor will be blinded to study assignment and the patients will be instructed to not reveal their status to the assessor.
- As the WRJ VAMC is a rural medical center that serves a large geographic area (New Hampshire and Vermont), we anticipate that several enrolled patients will prefer phone (or VA Video Connect) over in-person follow-up. Fortunately, the assessment instruments that we selected for this study can be administered over the phone or in person. Furthermore, our decision to allow patients to participate in study follow-up by phone (or VA Video Connect) or in person is consistent with the study methods of the original WHO BIC trials.

Summary of Project Work/Deliverables over the 4 year study period

- 1) Year 1: We will complete four deliverables during the first year:
 - A) Enroll 25 veterans in a randomized trial of VA BIC for patients being discharged from an inpatient mental health unit. (As described in the study

protocol above for patients recruited from Ground East)

- B) Develop an adapted version of the VA BIC for patients being discharged from an inpatient medical/surgical unit after receiving psychiatric consultation.
- C) Pilot an adapted version of VA BIC in 3 veterans being discharged from an inpatient Medical/surgical unit after receiving psychiatric consultation. (We will submit a study amendment prior to conducting this work)
- D) Develop an adapted version of VA BIC for patients being discharged from a residential substance treatment facility
- 2) Year 2: We will complete six deliverables during the second year: (*We will submit a study amendment prior to conducting the work described below*)

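### The five-point BSS benchmark is a within-patient change taken from the hospitalized-ambulatory gap; on Ground East both arms make that move, so it is not a between-arm effect size

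*Combined protocol and SAP*

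**What the plan says.** Specific Aims/Purpose, Preliminary Studies and Sample Size (under Statistical Considerations) give the same rationale. Five BSS points is held to be clinically meaningful because "it represents the mean difference in suicidal ideation between ambulatory and hospitalized psychiatric patients". The Primary Outcome paragraph turns this into a threshold for change: "an improvement of five points or more on the total BSS scores may be clinically relevant".

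The pilot is read against that figure. In nine treated veterans, "we found a greater than five-point improvement in the Beck Scale for Suicidal Ideation (BSS) over the three months following inpatient mental health discharge". The improvement is said to be significantly greater "compared to a matched group of historical controls participating in a post-mental health discharge qualitative study". From this, Sample Size concludes that 100 veterans, 25 per transition scenario, give enough power to show a clinically meaningful improvement overall and in each scenario. It gives no standard deviation, no numerical power and no between-arm target.

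On timing, Study Design says that "in most cases, the baseline assessment will occur on the day before discharge", in a private office on the inpatient unit. Follow-up is at one and three months, in both arms. Only the Ground East trial is open at present; the other three settings are to follow by amendment.

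**The concern.** The benchmark is a difference between two groups of patients, hospitalized and ambulatory. The plan uses it as an amount of improvement within patients. In the Ground East trial every participant, whichever arm they are in, belongs to the first group at baseline and to the second at follow-up. Controls also receive standard discharge care with safety planning and arranged follow-up visits, so some improvement without VA BIC is plausible. The benchmark cannot tell improvement that follows discharge from improvement caused by VA BIC.

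Two things are at stake. In interpretation, a mean gain of five points in the VA BIC arm could be described as clinically meaningful when standard care did as well. In planning, a before-after gain in treated patients stands in for the difference between arms, and the two are equal only if controls do not change.

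**Working it through.** **1. The plan's own figure.** The inputs are 25 patients per scenario and 100 overall, equal allocation, significance at P < 0.05 (taken as two-sided) and a benchmark of 5 points. With no SD or power stated, the sample size cannot be reproduced. It can only be back-solved. If 5 points were the between-arm difference, 80% power by the normal approximation needs

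SD ≤ 5 / [(1.960 + 0.842) × √(2/n per arm)].

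- 12.5 per arm: 5 / (2.802 × 0.400) = 4.46
- 50 per arm: 5 / (2.802 × 0.200) = 8.92

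The documents do not say whether the SD lies below these values.

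**2. What the pilot gain measures.** Between-arm effect = VA BIC change − control change. Sample Size gives the first term as more than 5 points. The second term, and the size of the difference from historical controls, are not given. The effect therefore cannot be recovered from the text.

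**3. Effect on planning (assumptions).** Let f be the share of a 5-point gain that controls also show. The between-arm difference is Δ = 5(1 − f). Power is for a two-sample t-test with 12 versus 13 patients:

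- √(1/12 + 1/13) = 0.4003
- noncentrality = Δ / (0.4003 × SD)
- 23 degrees of freedom, critical value 2.069

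At SD 5, the noncentrality is 5/2.002 = 2.50 for f = 0 and 2.5/2.002 = 1.25 for f = 0.5.

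| f (assumed) | Δ | SD 5 | SD 7 | SD 9 |
|---|---|---|---|---|
| 0 | 5.00 | 66.7% | 40.1% | 26.5% |
| 0.25 | 3.75 | 43.5% | 25.0% | 17.0% |
| 0.5 | 2.50 | 22.4% | 13.7% | 10.2% |
| 0.75 | 1.25 | 9.2% | 7.1% | 6.3% |

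Neither f nor the SD is in the documents. The table shows how sensitive the power claim is, not what will happen.

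**4. Effect on interpretation (assumptions).** Suppose VA BIC has no effect and both arms fall by a true mean of 5 points.

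- Each arm's observed mean gain reaches 5 points with probability of about 0.5, because the true mean sits on the benchmark.
- A two-sample t-test on change between arms (12 versus 13) rejected in 4.4% to 5.7% of 4,000 simulated trials per setting, with SD 5 to 9 and within-person correlation 0.3 to 0.7. That is the nominal 5% within simulation error.
- An observed between-arm difference of 5 points or more in favour of VA BIC has probability 1 − Φ(5 / (0.4003 × SD of change)): 0.6%, 3.7% and 8.3% for SD of change 5, 7 and 9.

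Under this null, five points within an arm is an even chance. Five points between arms is uncommon. The same number carries a different meaning on the two scales.

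**The case against.** The strongest reply is that nothing in the plan turns on five points. The Aim 1 analyses contain no five-point criterion and no responder endpoint, and significance is P < 0.05. Aim 1 is worded as a comparison with standard discharge care alone, patients are randomized, and the pooled model includes study arm. A fall common to both arms cancels in a between-arm contrast, as step 4 shows. All of this stands. A reader might infer that the trial could succeed by its own rule with no VA BIC effect; the documents contain no such rule.

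A reader might also infer that controls will improve by five points. That does not follow. A mean gap between two patient groups may reflect who is admitted, and patients about to leave the ward may already have improved by baseline. The one piece of evidence on controls is the significant difference from historical controls, who came from a post-discharge study and so appear to have made the same move. It points away from equal improvement, although it is non-randomized and given without a size.

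Nor does the argument extend to all 100 planned participants. It fits the 25 from Ground East. It fits the medical and residential scenarios only loosely, and the emergency-room scenario not at all.

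What the reply does not supply is a between-arm BSS target, since none is stated anywhere. Its reliance on cancellation also needs a between-arm contrast, whereas the per-setting test for Aim 1 is described as change across time with no arm term named. That is a separate matter, but it means the analysis text does not make up for the benchmark.

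**Conclusion.** The point holds in a limited form. The plan's only benchmark for a meaningful BSS effect is a within-patient change, justified by a gap that both Ground East arms cross between baseline and follow-up. It cannot by itself identify a VA BIC effect, and the pilot gain cannot serve as the between-arm difference behind the power claim. The randomized comparison is not biased by this. The fault lies in how an effect would be described and in the basis for the sample size.

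Its size cannot be fixed from the documents, because the control-arm change and the SD are missing. Under the assumptions in step 3, a control share of one half cuts power in a single scenario by roughly a factor of three, to between 10.2% and 22.4%. A smaller share does less harm, and a share of zero leaves the implied five-point difference intact.

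**What to change.** In Specific Aims/Purpose, Preliminary Studies, the Primary Outcome paragraph and Sample Size:

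- State the clinically relevant effect as a between-arm difference in BSS at three months, adjusted for baseline, with a justified value. Five points may be kept only if it is argued for on that scale. Aim 2 already plans analysis of covariance for its continuous measures, so the form is familiar to the study.
- State that a within-arm improvement of five points or more is descriptive and will not be called a clinically meaningful effect of VA BIC.
- If a responder proportion is shown, show it for both arms with the between-arm difference and its confidence interval.
- Remove the step from the pilot's within-arm gain to adequate power, or restate it with the size of the difference from historical controls, the controls' change and an SD.

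The cost is wording only: no change to visits, instruments or enrolment. The stated rationale becomes less favourable, and the benchmark is harder to meet if controls also improve.
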